### **Pharmacodynamic Parameters**

Serum concentrations of keratan sulfate and change from the baseline at every time point will be summarized and corresponding listings will also be provided.

### **6.8 Other Safety Endpoints**

Other safety endpoint includes serum pregnancy test and KTP-001 Antibody and serum concentration of KTP-001 will be summarized and listed. Other tests of urine pregnancy test, HBsAg, anti-HCV, anti-HIV, KTP-001 Antibody and serum concentration will be listed as subject data listings. Line graphs of baseline and post-baseline values will be graphically displayed for each subject by cohort.

## 7.0 HANDLING OF MISSING VALUES AND OUTLIERS

All available safety and efficacy data will be included in data listings and tabulations. No imputation of values for missing data will be performed.

When laboratory test results are above or below the limit of quantification (i.e proceeded by a “<” or “>” sign, for example “<xx”), the numerical value, xx, will be used for calculation in summary tables.

Missing or partially date missing for AEs/TEAE:

if due to partial dates or times it is not possible to definitively conclude that an AE is not treatment emergent, then a conservative approach will be taken whereby it will be classified as a TEAE e.g. if the first dose of study drug is “13May” and the AE starts in “May”, then that AE will be classified as a TEAE, unless the AE stop date precludes this (i.e. the AE stop date is definitively prior to the first dose of study drug).

Missing or partially missing medication date and Prior or Concomitant Medication (CM) determination:

If due to partial dates it is not possible to categorize a medication as prior or concomitant, then a conservative approach will be taken whereby it will be classified as such e.g. if the first dose of study drug is “13May” and another medication is started in “May”, then that medication will be classified as both previous and concomitant, unless the medication stop date precludes one of these classifications.

Missing safety data will not be replaced, except for AE and CM dates as described above.

Adverse events with missing severity will be summarized as severe. Adverse events with missing causal relationship will be summarized as related.

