	
Efficacy (exploratory)
 
The following measures of efficacy after administration of study drug will be explored in this study:
 
 • Lower back pain and leg pain (measured by 11-point numerical pain scale) at baseline, on Day 1 pre-dose, at 2, 4, 6, and 24 hours post-dose, at all post-dose visits (Weeks 1, 2, 4, 6 and 13, Months 6, 9, 12, 18, 24 or early termination visit). • Use and amount of any pain medications (including extra acetaminophen) added to the subject's baseline pain regimen within the first 13 weeks post-dose. • Spinal flexion and tension (measured by straight-leg raising or femoral stretch test) at 6 and 13 weeks after injection of study drug or early termination visit. • Improvement in functional ability measured by ODI at 6 and 13 weeks after injection of study drug or early termination visit. • Improvements in QOL as measured by the Short Form (SF)-12 Health Survey at 6 and 13 weeks after injection of study drug or early termination visit. • Improvements in symptom severity as measured by the PGI-C scale at 6 and 13 weeks after injection of study drug or early termination visit.

	
Pharmacokinetics Blood samples for measures of serum concentrations of KTP-001 will be drawn pre-dose (just prior to administration of study drug), at 2, 4, 6, and 24 hours post-dose, and at the 1-, 2-, 4-, 6-, and 13-week follow-up visits or early termination visit.
 
Pharmacodynamics (exploratory) Blood samples for measures of serum concentrations of keratan sulfate will be drawn pre-dose (just prior to administration of study drug), at 6 and 24 hours post-dose, and at the 1-, 2-, 4-, 6-, and 13-week follow-up visits or early termination visit.

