#### 4.0 STATISTICAL CONSIDERATIONS

Statistical analyses will be performed using SAS software, version 9.3 or higher. The safety population will be used as the analysis population for the primary endpoints and all safety end points. Full analysis set and per protocol set will be used as the analysis population for secondary and exploratory efficacy endpoints.

Continuous data will be summarized using n, mean, median, standard deviation (SD), minimum value, maximum value, 95% confidence interval (CI) and, if appropriate, number of missing values. Unless noted otherwise, summaries will be produced by visit (where applicable) and cohort. Summaries by visit will be based on nominal reporting. If more than one value is reported at a scheduled visit, the value collected closest to the intended visit date will be used. In the case of a tie, the latest version will be summarized.

Categorical data will be summarized using n, percentages. Percentages will be calculated based on the number of non-missing values. The number of missing values will be presented as a separate category with no percentage, if 1 or more patients are missing data for the summary. Otherwise, all categories will be presented (even if no patients are counted in the category). Counts of zero in any category will be presented with percentage as (0%).

Precision of summary statistics:

- Integer – Sample size (n, N) and number of missing responses (if displayed).
- One additional decimal place than reported/collected on the case report form (CRF) – mean, median, confidence interval.
- Two additional decimal places than reported/collected on the CRF – standard deviation.
- Same number of decimal places as reported/collected on the CRF – minimum, maximum.
- Percentages – one decimal place.

All data will be presented on listings in order of dosing cohort, patient, assessment date/time and assessment (in order collected on eCRF, unless specified otherwise). For display purposes, cohort labels will be ordered from smallest to largest. Dates will be presented in the format DDMMYY. Times will be displayed in 24-hour clock format. Numbering of tables, figures and listings will follow ICH E3 guidelines.

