#### **6.7.1.4 Clinical laboratory tests**

Descriptive statistics (mean, standard deviation [SD], minimum, maximum, and n), including change from baseline (pre-dose value of the relevant treatment period) for laboratory parameters of hematology, serum chemistry, coagulation, and urinalysis will be presented for all scheduled time points by cohort. Laboratory test results will be listed and abnormal values outside normal ranges will be flagged.

If data permits, urinalysis (pH and specific gravity) will be summarized (mean, SD, median, minimum, maximum, and n) at each time point. Shift tables for laboratory parameters will be generated based on changes in National Cancer Institute Common Terminology Criteria for AE grade from baseline to worst post-baseline value.

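### The SAP's one quantification-limit rule enters `<xx` as xx and does not say whether it covers serum KTP-001 and keratan sulfate; if it does, means rise and SDs shrink wherever values are below limit

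*SAP*

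**What the plan says.** SAP 7.0 opens its rule with "When laboratory test results are above or below the limit of quantification" and concludes that "the numerical value, xx, will be used for calculation in summary tables". A result of `<xx` therefore counts as xx, and so does `>xx`. This is the only such rule in the SAP. BLQ and LLQ appear in the abbreviation list but in no other provision. The visible protocol text (12.6, 12.8, 12.9) has none either.

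Two assays that can return censored values are to be summarized. SAP 6.8 says that "KTP-001 Antibody and serum concentration of KTP-001 will be summarized and listed", although its next sentence puts the same items among those to be listed. The Pharmacodynamic Parameters paragraph of SAP 6.7.2 says: "Serum concentrations of keratan sulfate and change from the baseline at every time point will be summarized". Under SAP 4.0, continuous data get n, mean, median, SD, minimum, maximum and a 95% CI, by visit and cohort. Both analytes are sampled before dosing and out to Week 13 (Protocol Synopsis, Pharmacokinetics and Pharmacodynamics).

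SAP 9.0 removes the PK parameters planned in the protocol, while SAP 2.0 keeps KTP-001 pharmacokinetics as a secondary objective.

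**The concern.** The limit is the highest value that a `<xx` result can hold. Entering it in a mean can only raise the mean. It also pulls low values toward the rest, so the SD can only fall or stay the same. For KTP-001 the pre-dose sample is the awkward case, because a result that means 'not quantifiable' would be tabulated as a positive concentration before any drug was given.

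This matters because the Cmax, tmax and AUC analysis is gone, so the concentration table is the only numerical summary left for the PK objective. If low-dose or late samples are mostly below limit, the table would mainly report the assay limit. A reader comparing cohorts could not tell, because no count of below-limit values is required.

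**Working it through.** **1. Does the rule reach these analytes?** The texts point both ways.

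- Narrow reading: SAP 6.7.1.4 ("Laboratory test results will be listed and abnormal values outside normal ranges will be flagged") uses the term for hematology, chemistry, coagulation and urinalysis. KTP-001 and keratan sulfate are handled in other sections, and SAP 7.0 names neither.
- Wide reading: Protocol 16.1.3, headed for serum KTP-001 and antibody, speaks of laboratory tests. SAP 6.8 groups KTP-001 concentration with hepatitis, HIV and pregnancy tests.

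On the wide reading the limit is substituted. On the narrow reading the two analytes have no rule.

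**2. Inputs.** There are 6 subjects per cohort (Protocol Synopsis: 24 subjects in 4 cohorts). The documents give no LLQ, expected concentration or below-limit rate, so everything below is in LLQ units and conditional. There is no figure of the plan's own to reproduce.

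**3. All six below limit.** Mean = (6 × 1)/6 = 1.0 LLQ, SD = 0, CI width = 0. The true mean could lie anywhere from 0 to 1. With zero substituted, the mean is 0 and the SD is also 0.

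**4. Some below limit.** With k values below limit set to s, and the other 6 − k equal to m, the mean is [k·s + (6 − k)·m]/6.

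| m | k | s = 1 (SAP) | s = 0.5 | s = 0 | SAP vs 0 |
|---|---|---|---|---|---|
| 2 | 1 | 1.83 | 1.75 | 1.67 | +10% |
| 2 | 3 | 1.50 | 1.25 | 1.00 | +50% |
| 2 | 5 | 1.17 | 0.75 | 0.33 | +250% |
| 10 | 1 | 8.50 | 8.42 | 8.33 | +2% |
| 10 | 3 | 5.50 | 5.25 | 5.00 | +10% |
| 10 | 5 | 2.50 | 2.08 | 1.67 | +50% |

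For m = 2 and k = 3 the SDs are 0.55, 0.82 and 1.10.

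**5. Bias against a known truth.** Assume log-normal concentrations with a proportion p below limit. Let s² = ln(1 + CV²), z = the normal quantile of p, and M = exp(s²/2 − s·z), the true mean in LLQ units. Substituting c gives expected mean/true mean = c·p/M + Φ(s − z). For CV 50% and p = 0.5: s = 0.472, M = 1.118, and the SAP rule gives 0.5/1.118 + 0.682 = 1.129, or +12.9%. A simulation with 2,000,000 draws per setting gave these biases:

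| CV | p | Mean, c = 1 (SAP) | SD, c = 1 | Mean, c = 0.5 | Mean, c = 0 |
|---|---|---|---|---|---|
| 50% | 10% | +1.0% | −2.2% | −1.5% | −3.9% |
| 50% | 25% | +3.7% | −7.3% | −4.4% | −12.6% |
| 50% | 50% | +12.9% | −20.0% | −9.5% | −31.8% |
| 50% | 90% | +68.4% | −59.4% | −5.3% | −79.1% |
| 100% | 50% | +15.0% | −8.9% | −2.7% | −20.4% |
| 100% | 90% | +117.6% | −39.8% | +25.2% | −67.3% |

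**6. Change from baseline.** If the baseline is below limit and the post-dose value is 2 LLQ, the rule gives 2 − 1 = 1. The true change lies between 1 and 2. The understatement is at most one LLQ.

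**7. Upper limit.** For `>xx`, xx is the lowest value possible, so the mean is biased down.

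**The case against.** The strongest reply is that SAP 7.0 was probably written for clinical laboratory tests, that no below-limit rate is known, and that nothing decisive rests on these tables. Much of this stands. The study tests no hypothesis (SAP 3.4). The protocol describes dose escalation as resting on safety measures, including adverse events and laboratory values, and names no concentration mean. With a quarter or less of values below limit, the mean bias in step 5 is under 4%.

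Four stronger readings are tempting, and the documents do not support them.

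- A reader might infer that the SAP will inflate both means. That requires the wide reading and below-limit values. Doses start at 5 µg in a disc that Protocol 7.3 describes as a closed space, which makes low serum KTP-001 plausible. Nothing visible suggests that keratan sulfate falls below limit. Assay text in Protocol 10.1 and 10.3 is blacked out and may state a limit.
- A reader might blame this rule for the zero SD in an all-below-limit cohort. Any constant gives that, as step 3 shows.
- A reader might call the table the only PK analysis left. SAP 6.8 also keeps listings and individual line graphs, and SAP 7.0 alters summary tables only.
- A reader might prefer zero for KTP-001. Protocol 3.1 says that MMP-7 is endogenous, so zero may be wrong even before dosing. Step 5 shows that zero has its own, often larger, bias.

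What the reply does not remove is that a programmer who meets `<xx` in the concentration data finds only this rule, or none. Both cases need the same wording in SAP 7.0.

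**Conclusion.** The point holds in conditional form. The SAP does not say whether its single limit rule covers KTP-001 and keratan sulfate. If it does, the direction of bias is certain wherever values are below limit: means up, SDs down, and change from a below-limit baseline understated, with the reverse effect on the mean for `>xx`. The size depends on a censoring rate that the documents do not give. Under the log-normal assumption it is negligible at 10% below limit, about 13% to 15% of the mean at 50%, and 68% to 118% at 90% (CV 50% and 100%). An all-below-limit pre-dose cohort would show a KTP-001 mean equal to the LLQ.

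This should be corrected before the tables are programmed. It affects secondary and exploratory descriptive summaries, not the primary safety conclusions. Antibody is a separate matter: the objective is its presence, so a mean of censored values is not called for.

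**What to change.** In SAP 7.0:

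- Limit the xx substitution to the clinical laboratory tests of SAP 6.7.1.4.
- For KTP-001 and keratan sulfate, report n (%) below and above the quantification limits at each time point and cohort.
- Where more than half of the values are below limit, give no mean, SD or CI, and print the median and minimum as `<LLQ` when they fall among the censored values. With six subjects this means four or more below limit, and the median is then always `<LLQ`.
- Otherwise use one pre-stated substitution below the limit, for example LLQ/2, and repeat the summary at 0 and at LLQ. Treat change from baseline the same way. The choice is a convention, and the check shows whether it matters.
- Summarize antibody as the number and percentage positive.

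SAP 6.8 should also say once whether KTP-001 concentration is summarized as well as listed.

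The cost is SAP wording, one extra row per concentration table and the repeated summaries. Some tables, probably for the low-dose or late samples, may show no mean.

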## **8.0 INTERIM ANALYSIS**

No Interim analysis will be performed.

## **9.0 CHANGES FROM ANALYSIS METHODS PLANNED IN THE PROTOCOL**

The planned protocol analysis of PK parameters and summary on counting the rescue medications were removed.

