10.2 Pharmacokinetic Parameters

Pharmacokinetic variables will be calculated from the serum concentration data using noncompartmental methods (WinNonlin® Professional Network Edition, version 5.2 or higher, Pharsight Corp, Palo Alto, CA) and actual sampling times.

The following PK parameters will be determined:

C_{\max} Maximum observed serum concentration

t_{\max} The time that C_{\max} was observed

AUC_t Area under the concentration-time curve from time zero to time (t)

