12.8 Pharmacokinetic Analysis

Serum concentrations will be presented descriptively by time. All derived PK parameters will be presented with individual values and descriptive statistics. Serum anti-KTP-001 antibody detection will be presented descriptively by time.

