## 1.0 INTRODUCTION

The purpose of this document is to provide further details about the statistical analysis methods specified in the study protocol KTP-001-CL-101: a Phase 1/2, open-label, non-controlled, single ascending dose study to evaluate safety, tolerability, pharmacokinetics, and exploratory efficacy of KTP-001 in subjects with lumbar disc herniation. This statistical analysis plan (SAP) has been based on International Conference on Harmonisation (ICH) E3 and E9 guidelines and in reference to protocol version 4.1 amendment 4 dated 20October2015. The statistical analysis plan covers statistical analysis, tabulations and listings of safety and efficacy data.

Any major deviations from the methods specified in this document and the protocol will be discussed and documented.

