### Secondary objectives

The secondary objectives of this study are:

- To determine the PK of KTP-001 in the serum of circulating blood after intradiscal injection of study drug.
- To determine the presence of anti-KTP-001 antibody in the serum of circulating blood after intradiscal injection of study drug.

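### SAP 9.0 drops the protocol's PK parameters (Cmax, tmax, AUCt) without a reason while PK stays a secondary objective; its rescue-medication clause is also ambiguous

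*SAP*

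**What the plan says.** **PK in the protocol.** Section 10.2 commits to three parameters ("The following PK parameters will be determined": Cmax, tmax and AUCt) by noncompartmental methods with actual sampling times. Section 12.8 adds: "All derived PK parameters will be presented with individual values and descriptive statistics". Section 12.3 defines a PK Evaluable Population. The synopsis sets the sampling ("Blood samples for measures of serum concentrations of KTP-001 will be drawn pre-dose", then at nine later times up to Week 13).

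**PK in the SAP.** Section 2.0 keeps the secondary objective: "To determine the PK of KTP-001 in the serum of circulating blood after intradiscal injection of study drug". Section 9.0 then says: "The planned protocol analysis of PK parameters and summary on counting the rescue medications were removed". What remains is in 6.8, under other safety endpoints: "KTP-001 Antibody and serum concentration of KTP-001 will be summarized and listed", and "Line graphs of baseline and post-baseline values will be graphically displayed for each subject by cohort". Section 5.0 lists four populations, and the PK Evaluable Population is not among them. Section 1.0 gives the scope: "The statistical analysis plan covers statistical analysis, tabulations and listings of safety and efficacy data".

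**Rescue medication.** Protocol 8.2 plans two items, the number of subjects and the amount. SAP 6.7.2 keeps both, in its endpoint list and in its paragraph on rescue use. SAP 6.5 also summarizes rescue details by cohort, by the same method as concomitant medication, which is number and percentage of subjects.

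**The concern.** A secondary objective remains, the samples to answer it remain, and the analysis that would answer it is removed in one unexplained sentence. The removal was not carried through the SAP: its abbreviation list still defines Cmax, tmax, AUCt and the quantification-limit terms, and the loss of the PK population is not declared in 9.0.

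This is a first-in-human study over a 150/5 = 30-fold dose range. Peak and total serum exposure by dose are basic outputs of its PK objective. A reader of the report could not tell whether the parameters were dropped because they could not be estimated or for some other reason.

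On rescue medication, two analysts working from the same SAP could produce different tables.

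**Working it through.** There is no sample size, power or error rate to recompute, because the study has no hypothesis test. The check compares what was planned with what is left.

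**1. Are the data still collected?** PK times are pre-dose; 2, 4, 6 and 24 h; and Weeks 1, 2, 4, 6 and 13. That is 1 + 4 + 5 = 10 per subject, which reproduces the 10 PK samples in Protocol 11.16. For 24 subjects, 10 × 24 = 240 samples. SAP Appendix 1 keeps the KTP-001 sampling.

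**2. What was planned and what is left?**

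| Output | Planned in the protocol | In the SAP |
|---|---|---|
| Subject-level parameter values | 3 × 24 = 72 | none tabulated |
| of which AUCt | 1 × 24 = 24 | not reported; could be recomputed from listings |
| of which Cmax and tmax | 2 × 24 = 48 | can be read off listings or graphs |
| Parameter summaries across subjects | 3 × 4 = 12, if by cohort | 0 |
| Concentration summaries | by time | 10 × 4 = 40 cells if by time and cohort |

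Two entries rest on assumptions. Protocol 12.8 does not say by dose level, although 12.7 and 12.9 do, so 12 is an inference. SAP 6.8 does not say that concentrations are summarized at each hour. The default in SAP 4.0 is by visit and cohort. Pre-dose to 24 h all belong to Visit 1, so a literal reading gives 6 × 4 = 24 cells, and the SAP 4.0 rule for several values at one visit could then leave only one Day 1 value in the summary.

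**3. Can the retained summaries stand in for the parameters?** Partly. SAP 4.0 includes the maximum in every continuous summary. If the table is by time, the largest of those maxima is the cohort's highest observed Cmax. The mean Cmax is not recoverable in the same way: the highest of the by-time means is at most the mean of the individual peaks, with equality only if one sampling time attains every subject's peak. Neither tmax nor AUCt has any cohort statistic.

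**4. Does the handling of low values matter?** The only quantification-limit rule, in SAP 7.0, is written for laboratory test results and uses the limit itself as the value. Suppose it were applied to KTP-001 in a subject with every result below a limit L. The trapezoidal area to Week 13 would be L × (13 × 7 × 24) = 2,184 × L (in concentration × hours), and Cmax would be L, although nothing was quantified. The SAP does not say whether the rule applies.

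**5. What does the rescue clause remove?**

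| Reading of *counting* | Conflicts with |
|---|---|
| Amounts | SAP 6.7.2, endpoint list and rescue paragraph (2 places) |
| Subjects | the same two places and SAP 6.5 (3 places) |
| Tally of medications or records | nothing, necessarily |

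**The case against.** The strongest defence has four parts.

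- **The change is declared, and the information is kept.** Section 9.0 is the right place to declare it, all analyses are descriptive, and concentrations are tabulated, listed and graphed. This stands in part: a reader might infer that PK has been abandoned, and the documents do not support that. Keeping the raw material is still not the same as reporting the planned summaries.
- **PK may be analysed elsewhere.** SAP 1.0 covers safety and efficacy data, and the protocol assigns the parameters to WinNonlin while the SAP uses SAS. This is possible, but 9.0 says the analysis was removed, and no other plan is named. If one exists, a single citation settles the matter.
- **Escalation does not depend on PK.** A reader might infer that dose decisions were weakened. The documents do not show that. Escalation rests on review of safety measures by the DSMB, no PK parameter is named as a criterion, and the detailed criteria are in a charter that is not among the documents.
- **The rescue clause can be read harmlessly.** This stands. A reader might infer a proven contradiction with 6.7.2, but on the third reading there is none.

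It is also fair to say that omitting the PK population follows naturally from omitting the parameters. The assay text is redacted, so whether concentrations will be quantifiable cannot be judged, and no motive for the removal can be inferred.

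**Conclusion.** The PK point holds. The SAP removes the only PK parameters the protocol plans, gives no reason, cites no alternative, and keeps the objective and the sampling. The loss is 24 AUCt values with no planned output and every across-subject summary of Cmax, tmax and AUCt (12, on the assumption of a by-cohort layout and full enrolment of 24). Individual Cmax and tmax remain readable, and each cohort's highest concentration appears if the summary is by time. The secondary objective is therefore partly answered. The primary safety analysis is not affected, and no effect on escalation is shown.

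The rescue point holds as an ambiguity to be resolved: a conflict on two of three readings, none on the third.

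**What to change.** 1. Restore Cmax, tmax and AUCt with individual values and descriptive statistics by cohort, using actual sampling times as in Protocol 10.2, and add the PK Evaluable Population of Protocol 12.3 to SAP 5.0.
2. If the parameters cannot be estimated because most concentrations are below quantification, say so in 9.0 and report the number quantifiable at each time point and cohort. If PK is analysed under another plan, cite it.
3. State how KTP-001 concentrations below quantification are handled, so that the SAP 7.0 laboratory rule is not applied by default. Say in 6.8 that concentrations are summarized by sampling time and cohort.
4. Delete the rescue clause from 9.0, or name exactly which tally is removed, and make 9.0, 6.5 and 6.7.2 agree.

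The cost is SAP wording and, if the data allow, one noncompartmental run on the 10 samples per subject already scheduled. No new data are needed: Protocol 6.5.2 already has subjects record daily analgesic doses, including rescue acetaminophen, in their diaries.
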